## 1. INTRODUCTION

This appendix details the implementation of Response Evaluation Criteria in Solid Tumors (RECIST) 1.1 guidelines (Eisenhauer et al 2009) for the CC-16047 study with regards to Investigator assessment of tumor burden including protocol-specific requirements for this study.

## 2. DEFINITION OF MEASURABLE, NON-MEASURABLE, TARGET AND NON-TARGET LESIONS

Only patients with measurable disease at baseline should be included in the study.

Measurable disease is defined by the presence of at least 1 measurable (by RECIST 1.1) lesion which has not been previously irradiated. A tumor lesion in a previously irradiated field can be assessed as measurable disease provided the lesion has been deemed to demonstrate progression.

### **Measurable:**

A lesion, not previously irradiated per the protocol prior to enrollment, that can be accurately measured at baseline as  $\geq 10$  mm in the longest diameter (except lymph nodes which must have short axis  $\geq 15$  mm) with computed tomography (CT) or magnetic resonance imaging (MRI) and that is suitable for accurate repeated measurements. A tumor lesion in a previously irradiated field can be assessed as measurable disease provided the lesion has been deemed to demonstrate progression.

### **Non-measurable:**

- All other lesions, including small lesions (longest diameter  $< 10$  mm or pathological lymph nodes with  $\geq 10$  mm to  $< 15$  mm short axis at baseline).
- Truly non-measurable lesions include the following: bone lesions, leptomeningeal disease, ascites, pleural/pericardial effusion, inflammatory breast disease, lymphangitic involvement of skin or lung, or abdominal masses/abdominal organomegaly identified by physical examination that is not measurable by CT or MRI.
- Lesions  $< 2$  cm biopsied within the screening period (newly acquired tumor biopsy)
- Previously irradiated lesions that have not demonstrated progression
- Brain metastasis

### **Special cases:**

- Lytic bone lesions or mixed lytic–blastic lesions, with identifiable soft tissue components, can be considered measurable if the soft tissue component meets the definition of measurability. Blastic lesions are considered non-measurable.
- Cystic metastases can be considered measurable lesions if they meet the criteria for measurability from a radiological point of view, but if non-cystic lesions are present in the same patient, these should be selected as target lesions (TLs).

### **Target lesions:**

A maximum of 5 measurable lesions (with a maximum of 2 lesions per organ), representative of all lesions involved suitable for accurate repeated measurement, should be identified as TLs at baseline.

### **Non-target lesions:**

All other lesions (or sites of disease) not recorded as TL should be identified as NTL at baseline.

## 1. METHODS OF ASSESSMENT

The same method of assessment and the same technique should be used to characterize each identified and recorded lesion at baseline and during follow-up visits. A summary of the methods to be used for RECIST assessment is provided in *Table 1*, and those excluded from tumor assessments for this study are highlighted with the rationale provided.

**Table 1 Summary of methods of assessment**

Target lesions	Non-target lesions	New lesions
CT (preferred)	CT (preferred)	CT (preferred)
MRI	MRI	MRI
	Clinical examination	Clinical examination
	X-ray, Chest X-ray	X-ray, Chest X-ray
		Ultrasound
		Bone scan
		FDG-PET

CT: Computed tomography; FDG-PET: 18-Fluoro-deoxyglucose positron emission tomography; MRI: Magnetic resonance imaging.

### 3.1 CT and MRI

CT and MRI are generally considered to be the best currently available and reproducible methods to measure TL selected for response assessment and to assess NTL and identification of any new lesions.

In the CC-16047 study, the methods of assessment of tumor burden used at baseline and follow-up visits are contrast-enhanced CT/MRI of the neck, chest, and abdomen (including liver and adrenal glands). Any other areas of disease involvement should be additionally imaged based on the signs and symptoms of individual patients. CT examination with intravenous contrast media administration is the preferred method. MRI should be used where CT is not feasible or it is medically contra-indicated. For brain lesion assessment, MRI is the preferred method.

### 3.2 Clinical examination

In the CC-16047 study, clinical examination will not be used for assessment of TL. Clinically detected lesions can be selected as TLs if they are assessed by CT or MRI scans. Clinical examination can be used to assess NTL and to identify the presence of new lesions.

### 3.3 X-ray

In the CC-16047 study plain X-ray may be used as a method of assessment for bone NTL and to identify the presence of new bone lesions.

### **3.4 Ultrasound**

In the CC-16047 study, ultrasound examination will not be used for assessment of TL and NTL as it is not a reproducible method, does not provide an accurate assessment of tumor size and it is subjective and operator dependent. Ultrasound examination can, however, be used to identify the presence of new lesions. If new clinical symptoms occur and an ultrasound is performed then new lesions should be confirmed by CT or MRI examination.

### **3.5 Endoscopy and laparoscopy**

In the CC-16047 study, endoscopy and laparoscopy will not be used for tumor assessments as they are not validated in the context of tumor assessment.

### **3.6 Tumor markers**

In the CC-16047 study, tumor markers will not be used for tumor response assessments as per RECIST 1.1.

### **3.7 Cytology and histology**

In the CC-16047 study histology will not be used as part of the tumor response assessment as per RECIST 1.1.

### **3.8 Isotopic bone scan**

Bone lesions identified on an isotopic bone scan at baseline and confirmed by CT, MRI, or X-ray at baseline should be recorded as NTL and followed by the same method as per baseline assessment.

In the CC-16047 study, isotopic bone scans may be used as a method of assessment to identify the presence of new bone lesions at follow-up visits. New lesions will be recorded where a positive hot-spot that was not present on the baseline bone scan assessment is identified on a bone scan performed at any time during the study. The Investigator should consider the positive hot-spot to be a significant new site of malignant disease and represent true disease progression in order to record the new lesion. Confirmation by CT, MRI and X-ray is recommended where bone scan findings are equivocal.

### **3.9 FDG-PET scan**

In the CC-16047 study, 18-Fluoro-deoxyglucose positron emission tomography (FDG-PET) scans may be used as a method for identifying new lesions, according with the following algorithm:

New lesions will be recorded where there is positive 18-Fluoro-deoxyglucose uptake not present on baseline FDG-PET scan or in a location corresponding to a new lesion on CT/MRI at the same follow-up visit. If there is no baseline FDG-PET scan available, and no evidence of new lesions on CT/MRI scans then follow-up CT/MRI assessments should be continued, scheduled as per protocol or clinical indicated, in order to confirm new lesions.

---

 A positive FDG-PET scan lesion should be reported only when an uptake greater than twice that of the surrounding tissue is observed.

## 2. TUMOR RESPONSE EVALUATION

### 4.1 Schedule of evaluation

RECIST assessments will be performed using contrast-enhanced CT/MRI assessments of chest, abdomen, and pelvis. Additional anatomy should be imaged based on signs and symptoms of individual patients at baseline and follow-up. Baseline assessments should be performed no more than 28 days before start of study treatment, and ideally should be performed as close as possible to the start of study treatment. The first on-study scan should be performed after Cycle 3, before beginning Cycle 4 treatment. Subsequent scans should be performed every 3 cycles (approximately every 9 weeks) thereafter until confirmed objective disease progression as defined by RECIST 1.1 (irrespective of the reason for stopping treatment or subsequent therapy). The same method should be used for tumor measurement throughout therapy. After discontinuation of therapy scans will be performed every 12 weeks.

Additional assessments will be performed post confirmed objective disease progression for patients remaining on assigned treatment, re-treatment, or until subsequent cancer therapy according to the clinical study protocol. Any other sites at which new disease is suspected should also be adequately imaged at follow-up.

If an unscheduled assessment was performed and the patient has not progressed, every attempt should be made to perform the subsequent assessments at their scheduled visits. This schedule is to be followed in order to minimize any unintentional bias caused by some patients being assessed at a different frequency than other patients.

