**Table 2. Trial Treatment**

Drug	Dose/ Potency	Dose Frequency	Route of Administration	Regimen/ Treatment Period	Use
Pembrolizumab	200 mg	Q3W	IV infusion	Day 1 of each 3 week cycle	Experimental
Poly-ICLC	1.8mg/mL *	Twice weekly	Intramuscular injection	Day 0/1, 4, 8, 11, 15, 18 of each cycle	Experimental

\*Per manufacturer, drug product is now formulated at the original 1.8/mg/mL “dry” weight which is equivalent to 2.0mg/mL “wet” concentration of Poly-ICLC. This is a label correction for residual water of hydration in the lyophilized components and represents no change in the product or formulation, but simply a calculation correction.

The treatment to be used in this trial will follow the same regimen in both phases; all subjects will receive both poly-ICLC and pembrolizumab on Day 1 of each cycle. The Day 1 dose of poly-ICLC should be administered in the clinic for all cycles, in both phases. This will allow for assessment of AEs/SAEs and application of dose modifications, if needed, prior to dispensing drug for that cycle.

Trial treatment will be given for 17 cycles. If therapy is not interrupted this will be one year of therapy but therapy may extend for more than one year if interruptions are needed. A subject who, after completing 17 cycles of study treatment and, at that time, has a radiologic disease status of SD, PR or CR, may continue to receive study treatment without interruption for an additional year (up to a total of 35 cycles) of study treatment (Second Course Phase/Retreatment Period, section 7.2.13). See section 5.4.2, *Dose Administration*, for details regarding drug administration.

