**Table 3. Dose Modification Guidelines for Drug-Related Adverse Events**

Toxicity	Hold Treatment For Grade	Timing for Restarting Treatment	Treatment Discontinuation
Diarrhea/Colitis	2-3	Toxicity resolves to Grade 0-1	Toxicity does not resolve within 12 weeks of last dose or inability to reduce corticosteroid to 10 mg or less of prednisone or equivalent per day within 12 weeks
	4	Permanently discontinue	Permanently discontinue
AST, ALT, or Increased Bilirubin	2	Toxicity resolves to Grade 0-1	Toxicity does not resolve within 12 weeks of last dose
	3-4	Permanently discontinue (see exception below) a	Permanently discontinue
Type 1 diabetes mellitus (if new onset) or Hyperglycemia	T1DM or 3-4	Hold pembrolizumab for new onset Type 1 diabetes mellitus or Grade 3-4 hyperglycemia associated with evidence of beta cell failure	Resume pembrolizumab when patients are clinically and metabolically stable
Hypophysitis	2-4	Toxicity resolves to Grade 0-1. Therapy with pembrolizumab can be continued while endocrine replacement therapy is instituted	Toxicity does not resolve within 12 weeks of last dose or inability to reduce corticosteroid to 10 mg or less of prednisone or equivalent per day within 12 weeks
Hyperthyroidism	3	Toxicity resolves to Grade 0-1	Toxicity does not resolve within 12 weeks of last dose or inability to reduce corticosteroid to 10 mg or less of prednisone or equivalent per day within 12 weeks
	4	Permanently discontinue	Permanently discontinue
Hypothyroidism		Therapy with pembrolizumab can be continued while thyroid replacement therapy is instituted	Therapy with pembrolizumab can be continued while thyroid replacement therapy is instituted
Infusion Reaction	2 b	Toxicity resolves to Grade 0-1	Permanently discontinue if toxicity develops despite adequate premedication
	3-4	Permanently discontinue	Permanently discontinue
Pneumonitis	2	Toxicity resolves to Grade 0-1	Toxicity does not resolve within 12 weeks of last dose or inability to reduce corticosteroid to 10 mg or less of

			prednisone or equivalent per day within 12 weeks
	3-4	Permanently discontinue	Permanently discontinue
Renal Failure or Nephritis	2	Toxicity resolves to Grade 0-1	Toxicity does not resolve within 12 weeks of last dose or inability to reduce corticosteroid to 10 mg or less of prednisone or equivalent per day within 12 weeks
	3-4	Permanently discontinue	Permanently discontinue

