- Isolated Grade 3 electrolyte abnormalities that are not associated with clinical signs or symptoms and are reversed with appropriate maximal medical intervention within 3 days
- Grade 3 fever lasting  $\leq 24$  hours with or without medical therapy and is not considered a serious adverse event

**The period for definition of DLT will be the first 3 weeks of treatment.** Dosing interruptions are permitted in the case of medical / surgical events or logistical reasons not related to study therapy (e.g., elective surgery, unrelated medical events, patient vacation, and/or holidays). Subjects should be placed back on study therapy within 3 weeks of the scheduled interruption, unless otherwise discussed with the Sponsor. The reason for interruption should be documented in the patient's study record.

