 Baseline scans must be obtained within 28 days prior to the first dose of trial treatment. The first on-study scan should be performed after Cycle 3, before beginning Cycle 4 treatment. Subsequent scans should be performed every 3 cycles (approximately every 9 weeks). The same method should be used for tumor measurement throughout therapy. After discontinuation of therapy scans will be performed every 12 weeks.

 Archival tissue may be used for MSI testing; all other testing should be done on fresh tissue, if available. Fresh tissue biopsy at cycle 4, at end of treatment visit and during follow-up is **optional** for subject.

 Beginning with Amendment 4, tissue collection was expanded to include Phase 1 subjects; in previous protocol versions, tissue was only to be collected for Phase 2 subjects.

 Subjects who have a radiologic status of SD, PR or CR after completing 17 cycles of study therapy may continue without interruption for an additional year (up to a total of 35 cycles of trial treatment).

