#### 8.5.2 Analysis of Secondary Endpoints

- a. The adverse event profile will be presented by dose level of the combination treatment for the phase I portion.
- b. The progression free survival rate, overall survival rate and duration of response of recurrent metastatic MRP colon cancer to the combination of pembrolizumab and poly-ICLC administered at RP2D will be estimated along with the correspondent 95%

confidence interval. In addition, the 20-week PFS rate along with its 95% CI will be estimated and presented.

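### On-treatment scans follow cycle number rather than the calendar, so a dosing delay of more than 2 weeks before the second scan moves it past week 20 and can bias the secondary 20-week PFS rate upward

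*Combined protocol and SAP*

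**What the plan says.** Appendix 11.4, section 4.1 sets the first on-treatment scan by cycle: "The first on-study scan should be performed after Cycle 3, before beginning Cycle 4 treatment". It continues: "Subsequent scans should be performed every 3 cycles (approximately every 9 weeks) thereafter until confirmed objective disease progression". Footnote 10 of the Section 6 flow chart gives the same rule. Neither place gives a calendar anchor or a window in days. The only reference to calendar time is the parenthetical 9 weeks.

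Pembrolizumab is given on "Day 1 of each 3 week cycle" (Table 2). Section 5.3 plans 17 cycles and accepts that interruptions may stretch them beyond a year, which implies that the cycle count waits while dosing is held.

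Delays are permitted in three places:
- Table 3 ends treatment for many toxicities when "Toxicity does not resolve within 12 weeks of last dose", so a shorter hold is allowed.
- Section 5.4.1.2, on dose-limiting toxicity, covers interruptions unrelated to treatment: "Subjects should be placed back on study therapy within 3 weeks of the scheduled interruption".
- Section 5.4.2 and flow-chart footnote 1 allow shifts of up to 3 days per cycle.

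On the analysis side, Section 8.5.2 says that "the 20-week PFS rate along with its 95% CI will be estimated and presented". Section 8 has no rule for dating a PFS event or handling a late scan, and no sensitivity analysis for scan timing.

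**The concern.** Scan-detected progression becomes known only when a scan is done. If the imaging clock stops whenever dosing stops, a patient on hold is looked at later than a patient dosed on time and can be counted as progression-free for longer. Some holds are caused by toxicity, so the timing of assessment comes to depend on a consequence of treatment. The 20-week rate is exposed because its nominal supporting scan, at week 18, is only 2 weeks before the landmark. The control is historical (Section 1), so no concurrent arm shares the distortion.

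**Working it through.** **Inputs from the documents:** 3-week cycles (Table 2); scans before Cycle 4 and every 3 cycles after that (Appendix 11.4, section 4.1); hold limit 12 weeks from last dose (Table 3); landmark at week 20 (Section 8.5.2).

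**Assumptions, not in the documents:** exponential PFS, S(t) = 2^(-t/median), with median 9, 13 or 18 weeks; a share f = 10 to 30% of patients delayed; progression dated at the scan that detects it; nothing detected between scans.

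**1. The plan's own interval.** 3 cycles × 3 weeks = 9 weeks, so the stated figure is reproduced. With no delay, scan 1 is at week 9 and scan 2 at 6 × 3 = week 18. The margin to the landmark is 20 − 18 = 2 weeks.

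**2. What delays do.**
- A 3-week interruption before scan 2 moves it to 18 + 3 = week 21.
- A hold running to 12 weeks from the last dose delays the next cycle by 12 − 3 = 9 weeks. If the last dose is Cycle 4 (week 9), Cycle 5 falls at week 21, Cycle 6 at week 24, and the scan due before Cycle 7 at week 27. No scheduled scan falls between weeks 9 and 27.
- Six successive 3-day shifts, if they accumulate, add 18 days: 18 + 18/7 = week 20.6.

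**3. Effect on the 20-week rate.** Under the assumptions, the observed rate is S at the last scan on or before week 20. An undelayed patient contributes S(18). A patient delayed by more than 2 weeks between scans 1 and 2 contributes S(9). The excess is f × [S(9) − S(18)].

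| Median (weeks) | S(9) | S(18) | Difference | f = 10% | f = 20% | f = 30% |
|---|---|---|---|---|---|---|
| 9 | 0.500 | 0.250 | 0.250 | 2.5 | 5.0 | 7.5 |
| 13 | 0.619 | 0.383 | 0.236 | 2.4 | 4.7 | 7.1 |
| 18 | 0.707 | 0.500 | 0.207 | 2.1 | 4.1 | 6.2 |

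The last three columns are percentage points.

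**4. Delay before scan 1.**
- A 3-week delay puts the scans at weeks 12 and 21, so the delayed patient contributes S(12) = 0.397, 0.527 or 0.630. The difference from S(18) is 0.147, 0.144 or 0.130. For f = 10 to 30% the excess is 1.3 to 4.4 points.
- A 9-week delay puts scan 1 at 9 + 9 = week 18. The delayed patient contributes S(18) and the excess is zero.

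**5. Scale.** For 27 patients and a rate of 25 to 50%, the normal-approximation 95% half-width is 1.96 × √(0.25 × 0.75/27) = 16 points to 1.96 × √(0.5 × 0.5/27) = 19 points. An excess of 2.1 to 7.5 points is 27 × 0.021 = 0.6 to 27 × 0.075 = 2.0 patients.

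**The case against.** Several stronger readings are tempting, and the documents do not support them.

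- A reader might infer from Table 3 that a cycle can slip by 12 weeks. The limit runs from the last dose, so a single hold costs at most 9 weeks against schedule.
- A reader might infer that every delay over 2 weeks inflates the rate by the full amount. Steps 3 and 4 show that this holds only when the delay falls between scans 1 and 2.
- A reader might take the aim to "minimize any unintentional bias caused by some patients being assessed at a different frequency than other patients" as a promise of equal calendar spacing that the protocol then breaks. That sentence closes a paragraph about returning to schedule after an unscheduled scan. It shows that the bias is recognised, but it does not promise more than that.
- A reader might apply the 3-week interruption allowance directly to Phase 2. It is worded generally but sits in the Phase 1 dose-limiting-toxicity section. It concerns events unrelated to treatment, so it does not support a claim that all holds reflect toxicity.

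Other points also stand. Deaths count whenever they occur, and Appendix 11.4 foresees unscheduled assessments and imaging of suspected new sites, so some progression would be caught between scheduled scans. Dating progression at the detecting scan is an assumption: Appendix 11.4, section 4.4 fixes a date only for an equivocal new lesion that is later confirmed. A site could also follow the 9-week gloss and scan by the calendar. Finally, the 20-week rate is secondary and descriptive, and the possible shift is well inside its confidence interval.

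These points limit the size of the problem but leave the mechanism in place. No passage tells a site to scan on time when dosing is late.

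**Conclusion.** The concern holds in a limited form. Cycle-based imaging combined with permitted cycle delays leaves the week-18 scan only 2 weeks of slack before the 20-week landmark. A cumulative delay of more than 2 weeks accrued before scan 2 uses that slack up, makes assessment timing depend on holds, and can bias the 20-week PFS rate upward.

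Under the stated assumptions the excess is about 2 to 7.5 percentage points for delay between scans 1 and 2. It is smaller, down to zero, for delay before scan 1, and it is reduced further by deaths and by progression found on unscheduled scans. The direction follows from the schedule. The size does not, because the documents give neither the share of delayed patients nor the PFS curve.

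A reader might extend the concern to the primary endpoint. The documents do not support that: the sample size in Section 8.4 rests on response rates of 5% and 20%, and no scan date enters it. The response-rate test and N=27 are unaffected.

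**What to change.** In flow-chart footnote 10 and Appendix 11.4, section 4.1, replace the cycle-based wording. Schedule on-treatment scans at weeks 9, 18 and 27 and every 9 weeks after that, counted from Cycle 1 Day 1, each within 7 days, regardless of dose holds or cycle delays. The upper end of the window for the second scan is week 19, still before the landmark. For patients who stop and re-enter through the Second Course Phase (Section 7.2.13), restart the same calendar from the first retreatment dose.

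This keeps the protocol's own 9-week interval, changes no dosing rule and barely alters the number of scans. The costs are that a held patient's scan may not coincide with a dosing visit and that the reported PFS may be slightly less favourable.

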### 4.2 Target lesions

#### 4.2.1 Documentation of target lesions

A maximum of 5 measurable lesions, with a maximum of 2 lesions per organ (including lymph nodes), representative of all lesions involved should be identified as TL at baseline. Target lesions should be selected on the basis of their size (longest diameter for non-nodal lesions or short axis for nodal lesions), but in addition should be those that lend themselves to reproducible repeated measurements. It may be the case that, on occasion, the largest lesion does not lend itself to reproducible measurement in which circumstance the next largest lesion, which can be measured reproducibly, should be selected.

The site and location of each TL should be documented as well as the longest diameter for non-nodal lesions (or short axis for lymph nodes). All measurements should be recorded in millimeters. At baseline the sum of the diameters for all TL will be calculated and reported as the baseline sum of diameters. At follow-up visits the sum of diameters for all TL will be calculated and reported as the follow-up sum of diameters.

Special cases:

- For TL measurable in 2 or 3 dimensions, always report the longest diameter. For pathological lymph nodes measurable in 2 or 3 dimensions, always report the short axis.
- If the CT/MRI slice thickness used is  $>5$  mm, the minimum size of measurable disease at baseline should be twice the slice thickness of the baseline scan.
- If a lesion has completely disappeared, the longest diameter should be recorded as 0 mm.

- If a TL splits into two or more parts, then record the sum of the diameters of those parts.
- If two or more TLs merge then the sum of the diameters of the combined lesion should be recorded for one of the lesions and 0 mm recorded for the other lesion(s).
- If a TL is believed to be present and is faintly seen but too small to measure, a default value of 5 mm should be assigned. If an accurate measure can be given, this should be recorded, even if it is below 5 mm.
- If a TL cannot be measured accurately due to it being too large, provide an estimate of the size of the lesion. Although a visit response of PD will be assigned in the vast majority of these cases, a case should be flagged and reviewed by the Study Physician in a blinded fashion if use of the estimated size in the calculation of TL would not give an overall visit response of PD.
- When a TL has had any intervention eg, radiotherapy, embolization, surgery, during the study, the size of the TL should still be provided where possible.

